It provides information about procedures for entering participants into the study, and provides sufficient detail to enable: an understanding of the background, rationale, objectives, study population, methods, statistical analyses, ethical considerations, dissemination plans and administration of the study; replication of key aspects of study methods and conduct; and appraisal of the study's scientific and ethical rigour from the time of ethics approval through to dissemination of the results. Every care has been taken in drafting this protocol, but corrections or amendments may be necessary. These will be circulated to registered investigators in the study. Sites entering participants for the first time should confirm they have the correct version through a member of the study team at UCL CCTU.

1.1 Compliance

The study will be conducted in compliance with the approved protocol, the Declaration of Helsinki (2008), the principles of Good Clinical Practice (GCP) as laid down by the Commission Directive 2005/28/EC with implementation in national legislation in the UK by Statutory Instrument 2004/1031 and subsequent amendments, the UK Data Protection Act, and the National Health Service (NHS) Research Governance Framework for Health and Social Care (RGF). International sites will comply with the principles of GCP as laid down by ICH topic E6 (Note for Guidance on GCP), Commission Directive 2005/28/EC, the European Directive 2001/20/EC (where applicable) and other national and local applicable regulations. Agreements that include detailed roles and responsibilities will be in place between participating sites and UCL CCTU.

1.2 Sponsor

KCL is the study sponsor and has delegated responsibility for the overall management of the SPREE study to UCL CCTU. Queries relating to KCL sponsorship of this study should be addressed to the Director of UCL CCTU, or via the study team.

1.3 Structured study summary

Source of Monetary or Material Support	National Institute for Health Research Efficacy and Mechanism Evaluation (EME) programme
Primary Sponsor	King's College London
Secondary Sponsor	Sponsor responsibilities for study management are delegated to UCL CCTU by the regulator, primary sponsor KCL.
Contact for Public Queries	[contact]
Contact for Scientific Queries	
[name] Harris Birthright Research Centre for Fetal Medicine, King's College Hospital, [name]. [contact] [contact] Email: [contact]
 
[name] Harris Birthright Research Centre for Fetal Medicine, King's College Hospital, [name]. [contact] [contact] Email: [contact]

Public Title	Screening programme for pre-eclampsia (SPREE)
Scientific Title	Screening programme for pre-eclampsia
Countries of Recruitment	United Kingdom
Health Condition(s) or Problem(s) Studied	Pre-eclampsia (PE)
Screening	All women with singleton pregnancies undergoing routine 11-13 weeks scan will be invited to participate in the screening study for PE.
Key Inclusion and Exclusion Criteria	
Inclusion criteria
 
 • Age \geq 18 years, • Singleton pregnancies, • Live fetus at 11-13 weeks of gestation, • Informed and written consent. 
Exclusion criteria
 
 • Women who are unconscious or severely ill, those with learning difficulties or serious mental illness. • Pregnancies complicated by major fetal abnormality identified at 11-13 weeks of gestation
Study Type	Multicentre prospective cohort study
Date of First Enrolment	April 2016
Target Sample Size	16,850
Primary Outcome(s)	The primary outcome will be the false positive and true positive frequencies for screening for PE using the Bayes theorem based method and for screening according to the NICE guidelines. The screen positive threshold applied to the risks will be determined by the NICE guidelines. It is anticipated that there will be an increase in detection rate for all-PE from 35% (NICE method) to 50% (mini-combined test), at false positive rate of 10%.

Key Secondary Outcomes	
Secondary outcome measures:
 
• To demonstrate an increase in detection rate for all-PE:
○ From 35% (NICE method) to 55% (combined test), at false positive rate of 10%;• To demonstrate an increase in detection rate for preterm-PE:
○ From 40% (NICE method) to 60% (mini-combined test), at false positive rate of 10%.○ From 40% (NICE method) to 75% (combined test), at false positive rate of 10%.
------------------------	---

1.4.2 Role of study sponsor and funders

Name	Affiliation	Role
National Institute for Health Research Efficacy and Mechanism Evaluation (EME) programme	N/A	Scientific peer review of the study proposal Provision of funds Study monitoring
King's College London (KCL)	N/A	Sponsor
The Comprehensive Clinical Trials Unit at UCL (UCL CCTU)	UCL	All Sponsor responsibilities delegated to UCL CCTU by KCL.

1.4.7 SPREE Partners

Name	Role and responsibilities
------	---------------------------

Perkin Elmer (Wallac Oy), Finland	Perkin Elmer will be responsible for the production and supply of PIGF reagents.
Roche	Roche will be responsible for the production and supply of PIGF reagents.
Thermo Fisher Scientific	Thermo Fisher Scientific will be responsible for the production and supply of PIGF reagents.

2 Study Diagram

CRL = Crown-Rump Length; MAP = mean arterial pressure; PI = pulsatility index; PAPP-A = pregnancy associated plasma protein-A; PLGF = placental growth factor

3 Abbreviations

β-hCG	β-human chorionic gonadotropin
CI	Chief Investigator
CI	Confidence interval
CRF	Case Report Form
CRL	Crown-rump length
CTU	Clinical Trials Unit
FMF	Fetal Medicine Foundation
GCP	Good Clinical Practice
ICH	International Conference on Harmonisation
IDMC	Independent data monitoring committee
IRB	Institutional Review Board
KCL	King's College London
MAP	Mean arterial pressure
Mat-CH	Maternal characteristics and medical history
NREC	National Research Ethics Committee
NT	Nuchal translucency
PAPP-A	Pregnancy associated plasma protein-A
PI	Principal Investigator
PIGF	Placental growth factor
PIS	Participant Information Sheet
PET	Pre-eclampsia
QA	Quality Assurance
QC	Quality Control
QP	Qualified person
REC	Research Ethics Committee
RR	Relative risk
SAP	Statistical Analysis Plan
SSA	Site Specific Approval
SMF	Study Master File
SMG	Study Management Group
SMT	Study Management Team
ToR	Terms of Reference
SSC	Study Steering Committee
UCL	University College London
Uterine artery PI	Uterine artery pulsatility index

4 Glossary of Terms

Adverse Outcome - a harmful outcome that is usually indicated by some result such as morbidity, mortality.

Algorithm - a formula or set of steps for solving a particular problem.

Aneuploidy - an abnormal number of chromosomes.

Cohort study - a study with two or more groups of people - cohorts - with similar characteristics. One group receives a treatment, is exposed to a risk factor or has a particular symptom and the other group does not. The study follows their progress over time and records what happens.

Crown-Rump length - is the measurement of the length of human embryos and fetuses from the top of the head (crown) to the bottom of the buttocks (rump).

Detection rate – the frequency of discovering a certain outcome from an analysis.

False positive rate - the frequency of a result that indicates that a given condition is present when it is not.

Fetus - the name for an embryo after 8 weeks of development

Hypertension (high blood pressure) - is a chronic medical condition in which the blood pressure in the arteries is elevated.

Impaired placentation – occurs when the placenta does not establish an adequate blood supply from the uterus.

Meta-analysis - a statistical method which can be used to combine the results of two or more studies.

Nuchal translucency - the thickness at the back of an unborn baby's neck. Measuring this thickness helps assess the risk of Down's syndrome and other abnormalities.

Patient demographics – they are objective characteristics of a population; e.g. age, marital status, family size, racial origin, present or prior disease, religion, income, and education.

Perinatal – refers to the period immediately before and after birth.

Placentation – the formation, type and structure or arrangement of placentas

Pre-eclampsia – a multisystem disorder of pregnancy associated with high blood pressure and proteinuria.

Prophylactic use – the use of a medication or a treatment designed to prevent a disease from occurring.

Prospective study - watches for outcomes, such as the development of a disease, during the study period and relates this to other factors such as suspected risk or protection factor(s).

Pulsatility index - a measure of the variability of blood velocity in a vessel.

Randomised control trial - a study in which a number of similar people are randomly assigned to two (or more) groups to test a specific drug or treatment. One group (the experimental group) receives the treatment being tested, the other (the comparison or control group) receives an alternative treatment, a dummy treatment (placebo) or no treatment at all. The groups are followed up to see how effective the experimental treatment was.

Relative risk - the ratio of the risk of disease or death among those exposed to certain conditions compared with the risk for those who are not exposed to the same conditions. If both groups face the same level of risk, the

relative risk is 1. If the first group had a relative risk of 2, participants in that group would be twice as likely to have the event happen. A relative risk of less than one means the outcome is less likely in the first group.

Screening – investigations that aim to find serious health conditions early, before any symptoms develop.

Uterine artery Doppler scan – ultrasound assessment of the blood flow in the vessels that supply the uterus.

5 Introduction

5.1 Background and Rationale

Background:

Existing research:

Current recommendation of screening for PE

PE, which affects about 2% of pregnancies, is a major cause of maternal and perinatal morbidity and mortality. PE can be subdivided into preterm-PE, requiring delivery <37 weeks' gestation and term-PE with delivery \geq 37 weeks. Preterm-PE is associated with a higher incidence of adverse outcome. The current guideline from the National Institute for Health and Clinical Excellence (NICE) recommends that at the booking visit, women at high-risk or with more than one moderate risk factor for PE should be identified and they should be advised to take low-dose aspirin daily from 12 weeks until the birth of the baby [1]. The performance of the current method of screening is poor and identifies only about 40% of the women that develop preterm-PE and 35% of all-PE.

Prevention of PE by low-dose aspirin

The evidence of benefit from prophylactic use of low-dose aspirin is derived from meta-analyses of randomised studies, which reported a reduction in the prevalence by about 10% [2]. There is also some evidence from some studies on small number of cases suggesting that the beneficial effect of aspirin in women at increased risk of PE may be substantially increased if treatment is initiated before 16 weeks' gestation [3-5]. The extent to which this is true is currently being investigated by our multicentre study (CI [name]; ASPRE study funded by the FP7 of the European Commission), which is anticipated to report results by early 2017.

Prediction of PE

Extensive studies in the last decade have established that the best performance for early prediction of PE can be achieved by a combination of maternal characteristics and medical history (Mat-CH) together with the measurements of the mean arterial pressure (MAP), uterine artery pulsatility index (PI), serum placental growth factor (PIGF) and serum pregnancy associated plasma protein-A (PAPP-A) at 11-13 weeks' gestation (combined test) [6]. A combination of maternal factors, MAP and PAPP-A forms the mini-combined test.

We developed a new method of first-trimester screening for PE based on prospectively derived data from 60,000 pregnancies. The method uses a novel survival-time model based on Bayes' theorem to combine the prior information from Mat-CH with the biomarker multiple of the median (MoM) to estimate patient-specific risk for development of PE [7,8]. This model has now been finalised based on data from 120,000 pregnancies. In the new model, the gestational age at the time of delivery for PE is treated as a continuous rather than categorical variable, offering the option to clinicians and researchers to select their own gestational age cut-off to define the high-risk group that could potentially benefit from therapeutic interventions starting from the first trimester.

The four biomarkers used in the model have been extensively investigated and are readily available for clinical use. Research by our group has led to the development of protocols for standardised and auditable measurements of MAP, uterine artery PI, PAPP-A and PIGF [9-12]. Reproducible measurements of PAPP-A and PIGF can be undertaken using automated platforms that are currently used for provision of screening for Down's syndrome in all maternity hospitals in the England.

Our research has also established that the performance of screening depends on firstly, characteristics of the study population (including racial group and prior history of PE), and secondly, adjustment of measurements of biophysical and biochemical tests for maternal and pregnancy characteristics (expressed as multiple of median [MoM]). Extensive experience of [name], who is responsible for Quality Assurance for the UK Down's syndrome screening programme of the National Screening Committee, has highlighted firstly, the

importance of training and audit in the use of biophysical tests and secondly, need for monitoring median levels and adjustment of values of biochemical tests according to reagents provided by different manufacturers.

The first trimester combined test for PE screening, using a novel Bayes-based method, is likely to be superior to the current method recommended by NICE based on Mat-CH. The estimated detection rates, for false positive rate of 10%, of the NICE method are about 40% for preterm-PE and 35% for all-PE and the respective values for our combined test and mini-combined test are 75% and 55%, and 60% and 50%. Though the performance of the mini-combined test is lower, it is cheaper with no additional biochemical markers above standard of care.

This study is necessary to prospectively validate the proposed new tests for the screening of PE.

5.2 Objectives

The primary aim of the study is to compare screening for PE using a Bayes theorem based method with screening using current NICE guidelines. The reference standards will be PE defined according to the International Society for the Study of Hypertension in Pregnancy [13] and the American College of Obstetricians and Gynecologists [14]. If a participant fulfils the criteria for PE by one definition and not the other they will be considered to have developed PE.

The objectives of the study are:

- To evaluate the performance of the new method of screening for PE, which uses Bayes theorem to combine the prior information from Mat-CH with biomarker levels to estimate the patient-specific risk for PE leading to delivery before any pre-specified gestational age, compared to that of the current method recommended by the NICE. We anticipate that the new method of screening will substantially improve the early detection of PE in the first trimester of pregnancy and that this method will be such so that any potentially useful new biomarkers identified in the future would be easily incorporated into the algorithm. Quality assurance of biophysical and biochemical markers used in screening for PE will be continuously monitored. The primary outcome of this study is to demonstrate a significant improvement in the detection rate for PE with the use of the proposed screening method, as compared to that of the existing guidelines.
- To improve our understanding of the pathophysiology of PE, according to the severity of the condition. PE is thought to be the consequence of impaired placentation leading to placental hypoxia and release of inflammatory factors. These cause platelet and endothelial cell activation leading to the development of the clinical signs of the disease. We will investigate biomarker profiles in pregnancies complicated by PE of different severity, as reflected in the gestational age at delivery and neonatal birth weight, from data we have already collected longitudinally at 11-13 weeks' gestation (n=120,000), 20-24 weeks (n=65,000) and 30-34 weeks (n=30,000).

5.3 Study Design

This is a prospective cohort study in at least six NHS hospitals.

Multicentre study comparing performance of an alternative method for screening for pre-eclampsia with that used currently (NICE)

To achieve results representative of what would happen in practice, a single gate multicentre prospective, cohort study of 16,850 pregnancies in at least six centres will be undertaken.

Training of healthcare professionals in participating centres:

We will undertake training for recording of Mat-CH, performing measurement of MAP [9] and uterine artery PI [10], collecting and analysing blood for PAPP-A and PIGF, calculating patient-specific risk for PE and recording pregnancy outcome to ensure consistency across sites.

Maternal serum concentrations of PAPP-A and PIGF are measured using either the DELFIA XPRESS analyser (PerkinElmer Life and Analytical Sciences, Waltham, USA), BRAHMS KRYPTOR analyser (Thermo Fisher Scientific, Hennigsdorf, Germany) or Cobas analyser (Roche Diagnostics, Penzberg, Germany).

Clinical evaluation of new screening method:

The study will be coordinated by the Comprehensive Clinical Trials Unit at UCL (UCL CCTU). Our method will be examined in at least six NHS maternity hospitals. In these hospitals, all eligible women attending for their routine 11-13 weeks scan will be invited to participate. Where possible, the patient information sheet will be sent with the appointment letter to all potential participants. On arrival for the 11-13 weeks scan, eligible women will be counselled by a dedicated researcher or midwife and those who agree will provide written informed consent. The Mat-CH will be recorded, the MAP and uterine artery PI measured according to standardised protocols. Maternal blood will be collected for measurements of serum PAPP-A and PIGF according to standardised protocols. Risk for PE will be calculated.

In participating hospitals, the basis of recommending the use of aspirin is the NICE guidelines but the degree of adherence to these guidelines is expected to be variable. The results of the combined test for PE will not be provided to the patients or their obstetrician and midwives and these will not be used to influence management. We will record whether the participants are taking aspirin or not at the 11-13 week scan. The participants will make a hospital visit at 19-24 weeks for a second ultrasound examination as part of their routine care. Quality assurance of biomarkers will be undertaken on a monthly basis and each site will be given feedback according to the results generated by the quality assurance algorithm.

Mechanistic components of the study:

PE is thought to be the consequence of impaired placentation leading to placental hypoxia and release of inflammatory factors. These cause platelet and endothelial cell activation leading to the development of the clinical signs of the disease.

We will evaluate the longitudinal biomarker profiles (MAP, uterine artery PI, PIGF) in pregnancies complicated by PE, according to the severity of the condition as reflected in the gestational age at delivery and neonatal birth weight; from data we have already collected longitudinally at 11-13 (n=120,000), 20-24 (n=65,000) and 30-34 (n=30,000) weeks' gestation.

We will use samples from our existing bio-bank to continue our research into the pathophysiology of PE and discovery of new biomarkers. We have carried out metabolomics studies in maternal serum at 11-13 weeks' gestation and found significant changes from normal in a number of metabolites in pregnancies with PE, fetal trisomies and congenital cardiac defects [15,16]. We are validating these metabolomics markers to ascertain the impact on diagnostic accuracy when they are combined with our established biomarkers.

The study will be conducted in compliance with the protocol, the Declaration of Helsinki (1996), the principles of Good Clinical Practice (GCP). The study will be reviewed and approved by the National Research Ethics Committee (NREC) as well as applicable Hospital Trusts. The University College London Comprehensive Clinical Trials Unit (UCL CCTU) will manage the sponsors' responsibilities and Quality Assurance to ensure compliance with GCP.

6 Methods

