6.5 Participant Timeline

Study procedure by visit:

Screening Visit (11-13 week of pregnancy or CRL 45-84mm)

- Informed Consent
- Patient demographics
- Height and Weight
- Maternal medical and obstetric history
- Family history
- Drug history including aspirin intake
- Routine first-trimester scan
- MAP
- Uterine artery blood flow (transabdominal colour Doppler ultrasound)
- PAPP-A and PIGF measurements
- Risk calculation

Follow up visit: 19-24 week of pregnancy

- Routine anomaly scan

	11-13 weeks scan	19-24 weeks scan
Gestation (weeks)	11-13 or CRL 45-84mm	19-24
Patient information and characteristics	√	
Informed consent	√	
Measurement of weight and height	√	
Measurement of MAP	√	
Fetal ultrasound scan	√	√
Measurement of uterine artery PI	√	
Measurement of biochemical markers (PAPP-A and PIGF)	√	
Risk calculation	√	
Drug history including aspirin intake	√	

Laboratory Tests

At the time of the 11-13 weeks scan, 20mL of maternal blood will be taken for the measurement of biochemical markers using either the DELFIA XPRESS analyser (PerkinElmer Life and Analytical Sciences, Waltham, USA), BRAHMS KRYPTOR analyser (Thermo Fisher Scientific, Hennigsdorf, Germany) or Cobas analyser (Roche Diagnostics, Penzberg, Germany). At sites with available storage facilities, the remaining serum and plasma will be stored at -80°C for future studies on potential biochemical markers of pregnancy complications.

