6.8 Data Collection, Management and Analysis

6.8.1 Data Collection Methods

Patient information for this study will be entered into an electronic CRF. The main CRF will be held electronically only and will not be printed. The CRF will be composed of 3 parts:

CRF part 1 This part will include patient demographics, medical, obstetric and drug history, family history, measurement of MAP, collection of blood samples for biochemical testing, performance of an ultrasound scan to confirm the GA by the measurement of fetal CRL and measurement of the uterine artery PI; and risk for PE. Participants will be identified on CRFs by initials, patient code and site name, date of enrolment and the enrolling site-PI or fellow.

CRF part 2 will record details of the routine clinical visits and medical, obstetric and drug history at 19-24 weeks.

CRF part 3 will record details of pregnancy outcomes, details of labour, development of PE, neonatal birth weight and outcomes.

If a participant withdraws from follow-up a paper CRF will be completed. CRFs must be kept current to reflect the participant's status at each phase during the course of the study.

The CRFs will be the source documents of the study that must be available at all times for audit.

A participant identification record will be kept by each site-PI that would allow linking of the participant study number, participant name and date of birth for those included in the study along with participant contact information. This file will be kept electronically at sites.

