6.8.4.2 Statistical Methods – Outcomes

The purpose of the analysis is to compare performance of screening using the Bayes theorem based method with that using the NICE criteria. The difference will be tested at the one-sided 2.5% level.

The primary analysis will be of the prospective cohort of 16,000 patients. All patients with data on maternal characteristics, medical history and outcome will be included in the analysis. Risks will be calculated using the algorithm developed. These calculations will be fully pre-specified so that the prospective cohort can be used as an independent test data set.

The essential features of our primary analysis are as follows. The NICE criteria define a high-risk group by applying a set of rules to information on Mat-CH resulting in a binary (positive/negative) outcome for each pregnancy. These results will provide an overall screen positive rate of around 10%. We will firstly determine the threshold for the risks that gives the same number of screen positives as NICE. Secondly, we shall construct the 2 x 2 contingency table of counts by classifying each patient with PE according to the result from NICE and the risk assessment (Table 3). We shall then apply an extension of McNemars test that uses the difference between the counts of discordant pairs b and c. Under the null hypothesis of equality, these counts have the same expected value. Under the alternative hypothesis of superiority of the Bayes theorem based method to NICE, the expected value of c exceeds that of b.

Table 3: Classification of cases PE according to screening results.

		Bayes method	
		+	-
NICE	+	a	b
	-	c	d

A complication for any comparative study of PE is that, by converting true positives to false positives, treatment with aspirin reduces the incidence of PE in the treated group. If treatment is dependent on screening using a particular method, then the bias will reduce the apparent DR for that method. We have therefore developed a modification to McNemars test that incorporates an assumed relative risk for aspirin and individual level data on aspirin treatment. We will be classifying individuals according to treatment with aspirin as summarised in Table 4.

Table 4: Classification of cases PE according to screening results.

Untreated		Bayes method	
		+	-
NICE	+	a_0	b_0
	-	c_0	d_0

Treated		Bayes method	
		+	-
NICE	+	a_1	b_1
	-	c_1	d_1

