If aspirin reduces the incidence of PE by θ and the proportions of women in the population receiving aspirin are denoted by p_a , p_b , p_c and p_d in the cells corresponding to a, b, c and d then under the null hypothesis of no difference in DR the cell counts in Table 4 are to have expected values proportional to the probabilities in Table 5.

Table 5: Expected cell proportions according to treatment and test result.

Untreated		Bayes method	
		+	-
NICE	+	$1-p_a$	$1-p_b$
	-	$1-p_c$	$1-p_d$

Treated		Bayes method	
		+	-
NICE	+	$p_a(1-\theta)$	$p_b(1-\theta)$
	-	$p_c(1-\theta)$	$p_d(1-\theta)$

The modified test compares counts c_0+c_1 with b_0+b_1 . Under the null hypothesis of no difference in sensitivity, the expected counts is in the ratio $1-p_c\theta : 1-p_b\theta$ respectively. Note that if $p_c = p_b$ or $\theta = 1$ (aspirin is ineffective) this ratio is 1:1 and the test reduces to McNemars test. If $\theta < 1$ (aspirin reduces risk) and $p_b > p_c$ then the expected value of the counts is larger for c_0+c_1 than for b_0+b_1 and McNemars test is biased against NICE. Our approach to analysis is to take an external estimate of θ based on the best available evidence at the time to adjust the analysis for the effect of aspirin. A sensitivity analysis with respect to variations across a plausible range of θ (e.g. a 95% confidence interval) based on the evidence at the time will be presented. Point and estimates and 95% confidence estimates of DR and differences between DR adjusted for potential treatment effects will also be produced using the model described above. The primary comparison, will be a comparison between NICE and the mini combined test.

Primary comparisons are as follows:

- NICE vs. the mini-combined test for all-PE.
- NICE vs. the combined test for all-PE;
- NICE vs. the mini-combined test for preterm-PE;
- NICE vs. the combined test for preterm-PE.

Secondary comparisons are as follows:

- A. NICE vs. the Bayes risk assessment based on Mat-CH;
- B. Bayes risk assessment using Mat-CH vs. mini-combined test;
- C. Bayes risk assessment using Mat-CH vs. combined test;
- D. Mini combined test vs combined test.

For comparisons (B) – (C) a receiver operating characteristic curve (ROC) analysis, including comparison of areas under the ROC curve will be reported. All comparisons will be made with respect to all-PE and preterm-PE.

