7.10.2 Reproducible Research

The study protocol will be published on SPREE study website (www.fetalmedicine.org).

8 Ancillary Studies

9 Protocol Amendments

Substantial Amendment 1	
1.	Pregnancies complicated by major fetal abnormality identified at 11-13 weeks of gestation have been added to the exclusion criteria
2.	The date of first enrolment has been changed to the actual month.
3.	The name of the Study Manager and an additional member of the SMG have been added.
4.	Clarification that drug history including aspirin intake is required at the 11-13 week visit but not at the 19-24 weeks visit
5.	No tablet count of aspirin is required.
6.	Clarification that where possible, patient information sheets will be sent with the appointment letter to potential participants
7.	Clarification that all study site staff involved in data collection will possess certificates of competence from the FMF for non-routine measurements.
8.	The number of deliveries expected at the study sites / year has been clarified to an average number/site
9.	Analysis of blood samples for β -hCG is not included in study specific procedures

10.	Maternal medical and obstetric history is not required at 19-24 weeks. A routine anomaly scan is carried out only at this time point.
11.	Additional study site(s) to the six listed in Table 1 may be added.

10 References

1. National Collaborating Centre for Women's and Children's Health (UK). Hypertension in Pregnancy: The Management of Hypertensive Disorders During Pregnancy. London: RCOG Press, 2010.

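### Aspirin status is tied to the 11-13 week scan in 5.3 and 6.5 but not in 6.8.1; if only scan-day status is used, the aspirin-adjusted primary test may under-correct

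*Protocol*

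**What the plan says.** **When aspirin is recorded.** Section 5.3: "We will record whether the participants are taking aspirin or not at the 11-13 week scan". The 6.5 table has a row "Drug history including aspirin intake" ticked for the 11-13 week scan only, and the 19-24 week visit lists nothing but the routine anomaly scan. The amendment log in section 9 agrees with this current text: "Clarification that drug history including aspirin intake is required at the 11-13 week visit but not at the 19-24 weeks visit".

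**The conflicting statement.** Section 6.8.1: "CRF part 2 will record details of the routine clinical visits and medical, obstetric and drug history at 19-24 weeks". It does not name aspirin. CRF part 3, for outcomes, lists no aspirin item.

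**When aspirin starts, and for whom.** Section 5.1 reports that, for women NICE identifies at booking as being at increased risk, "they should be advised to take low-dose aspirin daily from 12 weeks until the birth of the baby". Section 5.3 adds that in the participating hospitals "the basis of recommending the use of aspirin is the NICE guidelines".

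**How it is used.** The modified McNemar test of 6.8.4.2 "incorporates an assumed relative risk for aspirin and individual level data on aspirin treatment". It compares the discordant counts c (Bayes positive only) and b (NICE positive only). "Under the null hypothesis of no difference in sensitivity, the expected counts is in the ratio" 1 − p_cθ : 1 − p_bθ, where p_b and p_c are the proportions receiving aspirin in those cells. The same section says that the unmodified test is biased against NICE when aspirin works and p_b exceeds p_c. The planned sensitivity analysis varies θ over a plausible range, for example a 95% confidence interval.

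**The concern.** The test needs exposure to aspirin during the pregnancy. Sections 5.3 and 6.5 collect a snapshot on the scan day, in a window that opens at 11 weeks, while the advised start is from 12 weeks. A woman scanned before she starts, or prescribed aspirin at or after the scan, is counted as untreated although aspirin may have prevented her pre-eclampsia.

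NICE status drives the advice, and Table 2 assumes 90% uptake in NICE positives against 10% in NICE negatives. If the missed users follow that pattern, p_b is understated by more than p_c. The null ratio moves towards 1:1, which is the uncorrected test that the protocol itself regards as unfair to NICE. The adjusted detection rates use the same model and would shift the same way. No analysis plan can recover exposure that was never collected.

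**Working it through.** **Inputs from the protocol.** 16,000 evaluable women (6.6) and 2% pre-eclampsia (5.1), so 320 cases before any aspirin effect. One-sided level 2.5% (6.8.4.2). Uptake 90%/10% and a 50% reduction (Table 2), with about 10% as the low end (5.1). θ is read as the proportional reduction, the only reading under which the stated null ratio works.

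**Assumed, not in the documents.** The share L of eventual users who start after the scan, and the overlap of the two tests among cases. A 25% reduction and 50%/10% uptake are added as intermediate settings.

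**Step 1: reproduce Table 2.** Simulate B ~ Poisson(320 × b × (1 − p_bθ)) and C ~ Poisson(320 × c × (1 − p_cθ)), with b and c the discordant cells as shares of cases before any aspirin effect. Test C against Binomial(B + C, q), where q = (1 − p_cθ) / [(1 − p_cθ) + (1 − p_bθ)], over 200,000 trials. A search over the overlap gave:

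| Difference | Table 2, 35% row | b = 7% of cases, exact test | Independent tests |
|---|---|---|---|
| 5 points | 33.4% | 33.7% | 18% |
| 10 points | 85.0% | 84.1% | 56% |
| 15 points | 99.3% | 98.7% | 88% |

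An overlap with b = 7% reproduces the table; independence does not.

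**Step 2: the null ratio.** Recorded uptake is true uptake × (1 − L).

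- L = 0: (1 − 0.10 × 0.5) : (1 − 0.90 × 0.5) = 0.95 : 0.55 = 1.73.
- L = 0.5: recorded uptake 45%/5%, giving 0.975 : 0.775 = 1.26.
- L = 1: 1 : 1, that is, plain McNemar.

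**Step 3: adjusted detection rate.** Take a true NICE rate of 35%. Relative to all cases without aspirin, observed NICE-positive cases are 0.35 × 0.55 = 0.1925 and NICE-negative cases 0.65 × 0.95 = 0.6175. With L = 0.5 the back-corrected values are 0.1925/0.775 = 0.248 and 0.6175/0.975 = 0.633, an estimated rate of 0.248/(0.248 + 0.633) = 28.2%. With L = 1 it is 0.1925/0.81 = 23.8%. At a 10% reduction the corresponding figures are 34.0% and 33.1%.

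**Step 4: type I error.** Set b = c, generate with true uptake and test with recorded uptake. Each entry is exact test / z version.

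| Uptake, reduction | Late share | b = c = 7% | b = c = 15% |
|---|---|---|---|
| 90/10, 50% | none | 1.6% / 2.0% | 1.9% / 2.3% |
| 90/10, 50% | 10% | 2.5% / 3.5% | 3.6% / 4.3% |
| 90/10, 50% | 25% | 4.7% / 6.1% | 8.5% / 10.2% |
| 90/10, 50% | 50% | 10.3% / 13.5% | 21.6% / 25.2% |
| 50/10, 50% | 50% | 4.2% / 5.4% | 6.7% / 8.1% |
| 90/10, 25% | 50% | 4.1% / 5.3% | 6.6% / 7.9% |
| 90/10, 10% | 50% | 2.5% / 3.3% | 3.2% / 3.9% |

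**Step 5: the other direction.** With a 50% reduction and b = c = 10%, recorded 90%/10% but true 70%/10% (stopping after the scan) gives 0.4%. Recorded 90%/10% but true 90%/30% (late starters only in cell c) gives 0.7%.

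**Step 6: can varying θ absorb it?** The ratio depends only on p × θ. If recording captures a fraction r of users in both cells, using θ/r restores it: with r = 0.5 and θ = 0.5, entering θ = 1.0 gives (1 − 0.05) : (1 − 0.45) = 0.95 : 0.55. For true θ of 0.25 or 0.10, the range would have to reach 0.50 or 0.20.

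**The case against.** The case against has four parts.

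**Recording may not stop at the scan.** Section 6.8.1 lists drug history at 19-24 weeks, and 6.8.4.2 does not tie p_a to p_d to the scan value. If CRF part 2 captures aspirin and the analysis uses it, most of the problem goes. This stands, so scan-only recording cannot be asserted as fact. What is certain is that the protocol gives two answers for a variable in its primary test.

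**The size rests on an assumption.** No section gives the late-start share. NICE identification is at booking, so women scanned at 12-13 weeks may already be taking aspirin. Section 6.6 itself presents the 90%/10%, 50% setting as its most extreme case. This stands: at a 10% reduction the inflation is small. A reader might assume that the two tests are independent among cases and reach 14% with a quarter late or 38% with half late. Step 1 shows that this overlap does not reproduce Table 2, so those figures are not used.

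**The direction can reverse.** A reader might infer that the primary test is certainly biased towards the Bayes method. The documents do not support that: it requires late starters to be mainly NICE-positive, which 5.3 and 6.6 presume but do not establish, and stopping after the scan works the opposite way.

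**The θ analysis may help.** A reader might infer that varying θ can never repair the error. Under proportional under-recording that is wrong, as step 6 shows. The remaining criticism is that a range built from a confidence interval for the effect of aspirin need not reach θ/r, and nobody will know r.

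**Conclusion.** The point holds in conditional form. Sections 5.3 and 6.5 contradict 6.8.1 on whether drug history is taken at 19-24 weeks; this needs no assumption.

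If the 5.3/6.5 rule is followed, users who start at or after the scan count as untreated. If they are mainly NICE-positive, the primary test and the adjusted detection rates may favour the Bayes method. By the exact test, in the Table 2 setting with discordant cells of 7-15% of cases, type I error is about 10-22% with half late and about 5-9% with a quarter late, against 2.5% nominal. With half late it is about 4-8% at a 25% reduction and about 2.5-4% at a 10% reduction, counting both versions of the test. All of these rest on an assumed late-start share and an assumed overlap. Scan-day data alone cannot show which case applies, so the matter should be settled while exposure can still be collected.

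**What to change.** 1. Reconcile 5.3, 6.5 and 6.8.1 on when aspirin use is recorded.
2. Record aspirin use after the scan: yes/no, gestation started, and gestation stopped if known. Use CRF part 2 at the routine 19-24 week visit, or the maternity record when CRF part 3 is completed. For women already past 19-24 weeks, use the record.
3. Define p_a to p_d in 6.8.4.2 from that exposure, and keep scan-day status as a sensitivity analysis.
4. Where later exposure cannot be obtained, pre-specify a sensitivity analysis over the share of unrecorded starters, alongside the one over θ.

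This concerns data collection only and changes nothing in clinical management. The cost is one or two extra CRF fields at a visit or record review that already takes place, some data entry, and an amendment reversing the earlier clarification on drug history.
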